4.5 Pooling of sites

Not foreseen.

4.6 Interim analyses

No formal interim analysis is planned for the study.

4.7 Handling of missing and incomplete data

Missing values will be included in the denominator count when computing percentages. The number of patients with missing data will be presented under the “Missing” category, if present.

Only the non-missing values will be evaluated for computing summary statistics.

Missing or incomplete data will be treated as described in chapters 5, 6, 7 and 8.

Forms			
Title	Statistical Analysis Plan Template		
Code	Version	Effective Date	Page
FRM_ST03_032	02	02 Oct 2017	13 of 26

Other critical missing data will be discussed prior to database lock, if any. Decisions will be taken during the data review and will be fully documented in the Data Review Report.

4.8 Changes in the planned analysis

The following changes were implemented in this SAP with respect to the analyses planned in the protocol:

- P-values of paired t-tests will not be provided for the mean change from baseline because the information is considered redundant with the one provided by the 95% confidence intervals.
- Vital signs and physical examination data will be listed only.

4.9 Data Review Meeting

A Data Review Meeting will be held after Database lock and before the Database freeze.

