9.3. Populations for Analyses

The following populations will be considered for the analysis:

- **Randomized population:** all randomized patients.
- **Safety population:** all randomized patients who receive at least one administration of the study treatment in a given treatment period.
- **Intention-to-Treat population (ITT):** all randomized patients from the safety population with at least one available post-baseline efficacy evaluation during the treatment period.
- **Per-protocol population (PP):** all randomized patients from the ITT population without any major protocol deviations (e.g., wrong inclusions, forbidden concomitant medications, etc.). The exact definition of major protocol deviations will be discussed with the clinical team case by case during the review of the data and will be described in the Data Review Report.

The statistical analysis will be performed after database lock.

The primary efficacy variable will be analysed both in the ITT and in the PP populations. As this is a superiority study, the primary analysis population will be the ITT. All the other efficacy variables will be analysed in the ITT population only.

Analysis of safety variables will be performed on the safety population.

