9.4. Statistical Analyses

All statistical analyses will be undertaken by CROS NT S.r.l. (Verona, Italy) using SAS software, release 9.4 or higher (SAS Institute, Cary, NC, USA).

The following describes the statistical analysis as it is foreseen at the time of planning the trial.

A detailed Statistical Analysis Plan (SAP) will be described in a separate document to be completed after the protocol is finalised and before database lock.

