3.4 Randomization and blinding

All participants will be centrally assigned to randomized study intervention using an Interactive Web Response System (IWRS). Before the study is initiated, the log in information and instructions for the IWRS will be provided to each site.

The center will be considered as a unique stratifying factor, so the randomization will follow a balanced-block center-stratified design.

Study intervention will be dispensed at the study visits summarized in the Schedule of Activities (SoA).

Forms			
Title		Statistical Analysis Plan Template	
Code		Version	Effective Date
FRM_ST03_032		02	02 Oct 2017
		10 of 26	

This is an open-label study; however, the specific intervention to be taken by a participant will be assigned using an IWRS. The site will contact the IWRS prior to the start of study intervention administration for each participant. The site will record the intervention assignment on the applicable case report form.

Potential bias will be reduced by using central randomization.

Since this is an open label study, no unblinding procedures are foreseen.

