4.2.4 Per Protocol population (PP)

All randomized patients from the ITT population without any major protocol deviations.

The exact definition of major protocol deviations will be discussed with the clinical team case by case during the review of the data and will be described in the Data Review Report.

The primary efficacy variable will be analysed on the PP.

In case an error occurs in treatment allocation, the following rule will be followed: if a patient was randomised but received the incorrect treatment, he/she will be reported under his/her randomised treatment group for all analyses performed on the ITT population, but he/she will be reported under the treatment actually received for all analyses performed on the safety population. The patient will be excluded from the PP population.

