Time to first re-hospitalization and/or death will be analysed using the Kaplan-Meier estimator. The number of re-hospitalization and/or death-free patients at the beginning of the period, the cumulative number of patients with re-hospitalization and/or death at the end of the period and the probability of being re-hospitalization and/or death-free at the end of the period with the associate 95% CIs will be presented by treatment for the following study periods: (0-12] weeks, (12-24] weeks, (24-36] weeks and (36 weeks-EoT]. The point estimates and the relative 95% CIs will be

Forms			
Title	Statistical Analysis Plan Template		
Code	Version	Effective Date	Page
FRM_ST03_032	02	02 Oct 2017	18 of 26

presented by treatment for the 75th, 50th and 25th percentiles. Comparison between treatments will be performed using the log-rank test stratified by center.

The LABD(s)+ICS group will be declared to prolong time to first re-hospitalization and/or death, compared to the LABD(s) group, if the difference between the two treatments is significantly in favour of LABD(s)+ICS (i.e., the p-value from the log-rank test is ≤ 0.050).

Plots of first re-hospitalization and/or death-free survival by treatment will also be presented.

The following SAS[®] code will be used to provide the Kaplan-Meier estimates for time to first re-hospitalization and/or death:

```
proc lifetest data=dataset TIMELIST=(12 24 36 EOT_A, EOT_B);
time TIME*EVENT(1);
strata CENTER / group=TMT;
run;
```

where TIME represents the time to first re-hospitalization and/or death or time to censoring, EVENT the censoring indicator (1 = censored patient), CENTER the center and TMT the treatment group; EOT_A, EOT_B, have to be replaced by the last time to first re-hospitalization and/or death or last time before EOT for each treatment group (if any).

Time to first re-hospitalization and/or death will also be analyzed using a Cox proportional hazards regression analysis with center and treatment group as qualitative independent variables and age as quantitative independent variables. The inclusion of any other potential confounding factors in the model will be evaluated during the Data Review, verifying the homogeneity of factors distributions among treatment groups.

The number of patients and the number of patients considered in the model will be provided by treatment. P-values of the independent variables based on Wald chi-square test will also be presented.

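### SAP 4.9 puts the Data Review Meeting after database lock, in conflict with SAP 4.7 and protocol 9.4.4 on critical missing data, so Per Protocol and Cox covariate choices can also fall after lock in an open-label trial

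*SAP*

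**What the plan says.** On the meeting, SAP 4.9 has one sentence: "A Data Review Meeting will be held after Database lock and before the Database freeze".

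On missing data, SAP 4.7 says "Other critical missing data will be discussed prior to database lock, if any" and continues: "Decisions will be taken during the data review and will be fully documented in the Data Review Report". Protocol 9.4.4 says the same in nearly identical terms.

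Two other choices are left to the review. On the Per Protocol set, SAP 4.2.4 says "The exact definition of major protocol deviations will be discussed with the clinical team case by case during the review of the data"; protocol 9.3 agrees. On the Cox model, which already holds center, age and treatment, SAP 7.1 says "The inclusion of any other potential confounding factors in the model will be evaluated during the Data Review, verifying the homogeneity of factors distributions among" the treatment groups; protocol 9.4.6 agrees.

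The protocol gives two markers around lock. Section 9.4: "A detailed Statistical Analysis Plan (SAP) will be described in a separate document to be completed after the protocol is finalised and before database lock". Section 9.3: "The statistical analysis will be performed after database lock".

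On masking, SAP 3.4 says "Since this is an open label study, no unblinding procedures are foreseen". SAP 4.8, which lists departures from the protocol, mentions paired t-tests and the listing of vital signs and physical examination data, but nothing about the timing of the review.

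**The concern.** The SAP gives two orders for one activity. A data manager who follows 4.9 locks first and reviews afterwards; one who follows 4.7 raises the critical missing-data questions before locking.

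The order matters because the review makes analysis decisions: who is in the Per Protocol set, how critical gaps are handled, and which covariates join the model that supplies the planned hazard ratio. Arm is known throughout an open-label trial. After lock, complete event data can be set beside it, and neither document asks for masked listings. Choices made in that position can be influenced by the result, and a reader of the report cannot tell whether they were. At stake is how far the Per Protocol and Cox results can support the log-rank test.

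**Working it through.** The plan attaches no figure to this point, and its sample size is not touched by it. The check is first of the text, then of how large the effect of an informed choice could be.

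**Timing, side by side**

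| Item | Where | Timing stated |
|---|---|---|
| Data Review Meeting | SAP 4.9 | after lock, before freeze |
| Critical missing data: discussion | SAP 4.7, protocol 9.4.4 | before lock |
| Critical missing data: decision | SAP 4.7, protocol 9.4.4 | in the data review, recorded in its report |
| Major deviations, hence Per Protocol set | SAP 4.2.4, protocol 9.3 | in the data review; lock not mentioned |
| Extra Cox covariates | SAP 7.1, protocol 9.4.6 | in the data review; lock not mentioned |
| SAP completed | protocol 9.4 | before lock |
| Analysis | protocol 9.3 | after lock |

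1. The SAP describes only one review meeting, so I take the data review in 4.7 to be the meeting in 4.9. Row 1 then conflicts with rows 2 and 3 read together.
2. Because a freeze follows, lock in 4.9 might mean a provisional lock. That does not help: 4.7 uses the same word and puts the discussion on the other side of it.
3. Rows 4 and 5 carry no lock timing, so a post-lock meeting breaks no stated rule for them. It does leave two analysis choices open after the point by which protocol 9.4 wants the SAP complete.

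**Size of an informed covariate choice**

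Inputs: 928 patients (2 × 464, from the sample size section); about 11% with an event (assumed; the plan's rates average (9% + 15%)/2 = 12%); no treatment effect; five binary prognostic factors, each with odds ratio 2 (assumed); logistic model. Five optional factors give 2^5 = 32 adjusted models. Two-sided type I error at a nominal 5%:

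| Null trials | Unadjusted | All five, fixed in advance | Smallest p of 32 | Only factors imbalanced between arms |
|---|---|---|---|---|
| 800 | 4.5% | 5.3% | 8.3% | not run |
| 3,000 (factor prevalence 50%, assumed) | 5.5% | 5.3% | 8.3% | not run |
| 12,000 | 4.9% | 5.1% | 8.0% | 4.8% |

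The last column adjusts for a factor when its imbalance has p < 0.10 or p < 0.05; these cut-offs are assumed, since the plan gives none, and both gave 4.8%. In the 3,000-trial run, counting only results that favour one named arm, smallest-p selection gave 4.4% against a nominal 2.5%.

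Simulation standard errors: √(0.083 × 0.917/800) = 1.0 percentage point; √(0.083 × 0.917/3,000) = 0.5; √(0.080 × 0.920/12,000) = 0.2. The 8% and 5% figures are clearly apart. The simulations cover covariate choice only, not Per Protocol membership or missing data, and use logistic rather than Cox regression.

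**The case against.** **The before-lock wording is narrow.** It covers critical missing data, and strictly it is the discussion that comes before lock; the decision belongs to the review. Someone could discuss before lock and decide after it. This is a possible literal reading, but it needs a separate pre-lock discussion that the SAP nowhere describes, and it leaves missing-data decisions after lock. The sections still need aligning. A reader might also infer that the documents require the Per Protocol and covariate decisions before lock; they do not.

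**Final outcomes by arm are not shown to be on the table.** A reader might infer that the reviewers will be working on final data split by arm. With lock and freeze undefined, and no description of what the meeting sees, the documents support only that nothing stated prevents it. This stands.

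**Timing is not the whole cause.** In an open-label trial, arm and events are partly known before lock, so moving the meeting does not by itself remove that knowledge. This stands, and is why masked listings belong in the fix.

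**The 8% figure describes a different rule.** The plan's criterion is homogeneity of factors between arms, not the treatment p-value, and selection of that kind showed no inflation. Picking by p-value could also happen before lock. Both points stand. What remains is that no list of candidate factors and no cut-off is given, so discretion is left.

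**The main conclusion is protected.** Success is declared on the center-stratified log-rank test in the ITT set, with event and censoring times defined in SAP 7.1. This stands, with one small gap: SAP 7.1 has no rule for a missing or partial admission or death date, so such a case could fall to the review.

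**Conclusion.** The conflict over critical missing data is real, both within the SAP and between SAP 4.9 and protocol 9.4.4, and it is undeclared. This assumes that the review in 4.7 is the meeting in 4.9, which is the natural reading. It does not depend on what lock means.

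The consequence is an opening for outcome-informed choices in the Per Protocol, missing-data and adjusted Cox analyses. It is not evidence that such choices will be made. A reader might take the 8.3% as the trial's error rate; the documents do not support that. It is an upper-end illustration of deliberate selection by p-value under assumed inputs, it concerns the adjusted model and not the ITT log-rank test, and balance-based selection gave 4.8%. The point is worth correcting because the remedy is cheap and these results are meant to support the primary test.

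**What to change.** 1. Amend SAP 4.9 so that the Data Review Meeting is held, and the Data Review Report signed, before database lock, in line with SAP 4.7 and protocol 9.4.4. Define lock and freeze.
2. Settle deviation classes, analysis-set membership and missing-data rules, including partial event dates, from listings without treatment arm, inhaler name or outcomes by arm. Switches between regimens can be shown as a programmed yes/no flag without direction, so that reviewers stay masked.
3. Replace the homogeneity check in SAP 7.1 with a Cox covariate list fixed in the SAP before lock on prognostic grounds, or state that center and age are the only adjustments. Listings without arm cannot support a balance check, so step 2 needs this step.
4. State that no analysis decision is taken between lock and analysis; anything later is reported as post hoc.

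The cost is SAP wording, the preparation of masked listings and a small scheduling change for data management. The covariate check is lost, but center, age and the pre-chosen prognostic factors stay in the model. Data collection and treatment are unchanged.

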4.10 Software

All statistical analyses and data processing will be performed using Statistical Analysis Systems (SAS®) Software (release 9.4) on a Windows 7 operating system.

5. Evaluation of Demographic and Baseline Characteristics

5.1 Subject enrolment and disposition

Statistical analysis

Disposition of patients will be presented by treatment and overall for all subjects.

The number of patients included in each of the Randomised, Safety, ITT will be summarised for each treatment.

5.2 Protocol violations

Not foreseen.

5.3 Study discontinuations

Definitions and data conventions

Date of completion/discontinuation

Date of study completion will be the date of study end recorded in the study conclusion/withdrawal form.

If the date of study completion is missing, the date of last study visit performed (i.e. Date of Visit 6) will be used.

Forms			
Title	Statistical Analysis Plan Template		
Code	Version	Effective Date	Page
FRM_ST03_032	02	02 Oct 2017	14 of 26

Date of discontinuation will be the date of withdrawal recorded in the study conclusion/withdrawal form.

Statistical analysis

Randomised patients who completed the study will be presented by treatment and overall for the Randomised population. Randomised patients who discontinued from the study prematurely will also be presented with a breakdown of the reasons for discontinuation by treatment and overall for the Randomised population.

5.4 Demographics and baseline characteristics

Definitions and data conventions

Race

Race as it is recorded on the CRF will be considered. If more than one race is ticked, Race will be set equal to “Other”.

Body Mass Index (BMI) (kg/m²)

BMI will be calculated using the following formula:

$$\text{BMI} = \frac{\text{Body weight (kg)}}{\text{height (m)}^2}$$

Time since disease diagnosis

Time since disease diagnosis (years) will be calculated using the following formula:

$$\text{Time since disease diagnosis (years)} = (\text{Date of Visit 1} - \text{first COPD diagnosis} + 1)/365.25$$

Statistical analysis

The baseline demographic characteristics will be summarised by treatment and overall by means of descriptive statistics.

The following characteristics will be provided for the ITT population:

- Age (years)
- Sex (male/female)
- Ethnicity (Hispanic or Latino, Non-hispanic or non-latino, Not reported, Unknown)
- Race (White (Caucasian), Asian, Black or African American, American Indian or Alaska Native, Native Hawaiian or other Pacific Islander, Other)
- Weight (kg)
- Height (cm)
- BMI (kg/m²)
- Smoking status (Non-smoker, Ex-smoker, Current smoker)
- Number of pack-years
- Alcoholic consumption (Yes, No, Former)

- Average number of units/week
- Caffeine consumption (Yes, No, Former)
- Average number of cups of coffee/week
- Time since disease diagnosis (years)

5.5 Medical and surgical history

Definitions and data conventions

Medical history

A disease is considered as medical history if it is not ongoing at screening visit (“ongoing” box is not ticked).

Concomitant disease

A disease is considered as concomitant disease if it is ongoing at screening visit (“ongoing” box is ticked). Concomitant cardiovascular diseases will be considered as they are recorded on the CRF separate form.

Statistical analysis

Medical history and concomitant diseases will be coded using Medical Dictionary for regulatory activities (MedDRA) dictionary (version 21.0) and frequency distributions and percentages will be summarised by treatment group for the ITT by System Organ Class (SOC) and Preferred Term (PT).

Counts will be given for both SOC and PT by subject. Subjects experiencing more than one past/concomitant disease event will be counted only once within each SOC and PT.

Concomitant cardiovascular diseases (Heart Failure, Ischemic Heart Disease, Atrial Fibrillation) will be separately summarised by treatment group for the ITT through frequency distributions and percentages.

5.6 Prior and concomitant medications

Definitions and data conventions

Date of first randomised study medication intake

The date of first randomised study medication intake is the first Start date recorded in the Study Medications Log.

Previous/Concomitant

The following categories of medications will be identified:

- previous medication (stop date \leq date of first medication intake);
- concomitant medication (stop date $>$ date of first medication intake or ongoing);

In case of missing or incomplete dates not directly allowing allocation to any of the two categories of medications, a worst-case allocation will be done according to the available parts of the start and the end dates. The medication will be allocated to the first category allowed by the available data, according to the following order:

- concomitant medication;

Forms			
Title		Statistical Analysis Plan Template	
Code	Version	Effective Date	Page
FRM_ST03_032	02	02 Oct 2017	16 of 26

- previous medication.

Statistical analysis

Medications will be coded using World Health Organization Drug Dictionary (WHO DD), version March 2018 B3.

Previous medications and concomitant medications will be summarised by treatment group for the ITT through frequency distributions and Anatomical Main Group (1st level of the Anatomical Therapeutic Chemical (ATC) classification), Chemical Subgroup (4th level of the ATC classification) and Preferred Name.

Subjects experiencing more than one medication classified in the same category (previous medications, concomitant medications) within the same anatomical main group, chemical subgroup and preferred name will be counted only once.

5.7 Other baseline characteristics

Not foreseen.

6. Evaluation of Treatment Compliance and Exposure

6.1 Compliance to study drug and treatment

Compliance will be listed only.

6.2 Exposure to study drug

Not foreseen.

6.3 Evaluation of pharmacokinetics

Not foreseen.

7. Evaluation of Efficacy

7.1 Analysis of primary endpoint

Definitions and data conventions

First re-hospitalization and/or death

The event “first re-hospitalization and/or death” is identified as the first occurrence between the first re-hospitalization (as collected in the “COPD EXACERBATION FORM”) and death, if any of them occurred.

Time to first re-hospitalization and/or death

Forms			
Title		Statistical Analysis Plan Template	
Code		Version	Effective Date
FRM_ST03_032		02	02 Oct 2017
			17 of 26

In patients with at least one event, time to first re-hospitalization and/or death will be calculated as the weeks between baseline (Visit 2) and the date at which the first re-hospitalization (i.e., Date of admission/prolonged hospitalization in the ‘COPD Exacerbation Form’) and/or death occurs.

Time to first re-hospitalization and/or death (weeks) = (date of first re-hospitalization and/or death - Visit 2 + 1)/7

Patients without first re-hospitalization and/or death or who are discontinued before having it will be considered as “censored” at the end of the study visit (Visit 6) or at the time of the withdrawal during the treatment period (i.e., the date of withdrawal). For the analysis, the following formula will be applied:

Censoring time (weeks) = (date of Visit 6/withdrawal - Visit 2 + 1)/7

Time to first re-hospitalization and/or death for the sensitivity analysis.

The crossover occurrence is identified as patients that switch from one treatment group to the other adding or stopping ICS and it will be identified as protocol deviation.

In patients without the crossover occurrence , time to first re-hospitalization and/or death will be calculated as described above.

In patients with the crossover occurrence:

- if they experienced first re-hospitalization and/or death before or at the crossover occurrence date, time to first re-hospitalization and/or death will be calculated and considered as for the patients without the crossover occurrence;
- if they experienced first re-hospitalization and/or death after the crossover occurrence date, time to first re-hospitalization and/or death will be censored at the time of crossover occurrence;
- patients without first re-hospitalization and/or death will be considered as “censored” at the cross-over start date. For the analysis, the following formula will be applied:

Censoring time (weeks) = (date of cross-over start - Visit 2 + 1)/7

Primary efficacy analysis

Analysis will be performed on ITT population.

Time to first re-hospitalization and/or death will be analysed using the Kaplan-Meier estimator. The number of re-hospitalization and/or death-free patients at the beginning of the period, the cumulative number of patients with re-hospitalization and/or death at the end of the period and the probability of being re-hospitalization and/or death-free at the end of the period with the associate 95% CIs will be presented by treatment for the following study periods: (0-12] weeks, (12-24] weeks, (24-36] weeks and (36 weeks-EoT]. The point estimates and the relative 95% CIs will be

Forms			
Title	Statistical Analysis Plan Template		
Code	Version	Effective Date	Page
FRM_ST03_032	02	02 Oct 2017	18 of 26

presented by treatment for the 75th, 50th and 25th percentiles. Comparison between treatments will be performed using the log-rank test stratified by center.

The LABD(s)+ICS group will be declared to prolong time to first re-hospitalization and/or death, compared to the LABD(s) group, if the difference between the two treatments is significantly in favour of LABD(s)+ICS (i.e., the p-value from the log-rank test is ≤ 0.050).

Plots of first re-hospitalization and/or death-free survival by treatment will also be presented.

The following SAS[®] code will be used to provide the Kaplan-Meier estimates for time to first re-hospitalization and/or death:

```
proc lifetest data=dataset TIMELIST=(12 24 36 EOT_A, EOT_B);
time TIME*EVENT(1);
strata CENTER / group=TMT;
run;
```

where TIME represents the time to first re-hospitalization and/or death or time to censoring, EVENT the censoring indicator (1 = censored patient), CENTER the center and TMT the treatment group; EOT_A, EOT_B, have to be replaced by the last time to first re-hospitalization and/or death or last time before EOT for each treatment group (if any).

Time to first re-hospitalization and/or death will also be analyzed using a Cox proportional hazards regression analysis with center and treatment group as qualitative independent variables and age as quantitative independent variables. The inclusion of any other potential confounding factors in the model will be evaluated during the Data Review, verifying the homogeneity of factors distributions among treatment groups.

The number of patients and the number of patients considered in the model will be provided by treatment. P-values of the independent variables based on Wald chi-square test will also be presented.

Treatment effect will be presented as a hazard ratio with the associated 95% Wald CI and p-value.

The following SAS[®] code will be used to estimate the Cox proportional hazards regression model:

```
proc phreg data=dataset;
class CENTER TRT;
model TIME*EVENT(1) = CENTER TRT AGE / ties=exact;
hazardratio TRT / cl=wald;
run;
```

where TIME represents the time to first re-hospitalization and/or death or time to censoring, EVENT the censoring indicator (1 = censored patient), TMT the treatment group, CENTER the center and AGE the age.

The variable TMT will be ordered in SAS in the following order:

- 1 = LABD;
- 2 = LABD + ICS.

Forms			
Title	Statistical Analysis Plan Template		
Code	Version	Effective Date	Page
FRM_ST03_032	02	02 Oct 2017	19 of 26

If the option “ties=exact” requires a considerable amount of computer resources, the Efron approximation will be used (“ties=efron”).

A sensitivity analysis will also be carried out excluding efficacy data (i.e., hospitalization and death) collected after the crossover occurrence date. The same analyses described above will be repeated on this modified dataset.

Finally, the same analyses described above will be repeated in the subgroup of patients treated with triple therapy.

